Improving Resilience and Longevity for Workers Through Exercise Protocol

The Canadian workforce is aging. The most prevalent age group is 50-54 years and most of these Canadians will aim to continue working over the next 10 years¹. However, the impact of arthritis on aging Canadians compromises their ability to continue working². By 2031, over 2 million Canadians aged 45 to 64 years will have arthritis. Among those with arthritis, one of three is expected to be out of work³. This unemployment rate is worse than for any other chronic health condition³.

We aim to boost the ability of older adults with the most common arthritis, osteoarthritis (OA), to engage in the workforce for as long as they desire. Osteoarthritis targets older adults and currently affects 4.4 million Canadians, a number expected to grow to 10 million in the next two decades⁴. The disease causes degeneration of all joint tissues, most commonly in the knee and hip⁵. Further, OA affects the Canadian labour force: 30% of those with OA will experience difficulty at work⁴. Pain and immobility caused by OA result in frequent absences from work and, ultimately, lost productivity⁶.

Identifying strategies to promote productivity among older workers with knee and hip OA will be of great public health significance in the coming decades. However, we face two challenges. First, obesity among sedentary workers is a risk for worsening knee and hip OA. A five unit increase in body mass index is associated with a 35% increased risk of developing OA⁷. Second, large occupational loads on the knee and hip worsen OA. Pooled data from 66 studies (n=526,343) revealed that, compared to workers who stand, those required to frequently squat, kneel, and carry have over a 60% increased risk of worsening chronic pain⁸. Therefore to promote productivity, we must address obesity while minimizing exposure to large loads. Unfortunately, few studies have investigated strategies to improve productivity among aging workers with OA⁹. A systematic review showed that exercise has the most promise in achieving this goal because it reduces pain and sick time, and improves mental health⁹. By comparison, ergonomic interventions (e.g., mechanical patient lifts, ergonomic work-stations), and education yield a minimal effect on pain, sick time, or longevity in the workplace⁹. Not surprisingly, there is a call for studies examining exercise for the aging worker with knee and hip OA⁹.

RESEARCH PURPOSE AND SCOPE

The purpose of this study is to examine the impact of an OA-specific aerobic and strengthening exercise program, delivered within the workplace, on mobility, pain, physical capacity, and resilience among workers with knee or hip OA as well as those with no joint pain. We hypothesize that exercise designed for OA, delivered at work, will improve all of these outcomes.

METHODOLOGY

Participants

Participants will be women and men employed in administrative roles at Ford Motor Company in Oakville. All eligible participants will be welcome to participate.

Inclusion and Exclusion Criteria: We will recruit 40 participants from Ford. Inclusion criteria include part- or full-time employment in an administrative role at Ford. Men and women will be welcome. The exclusion criteria include a self-reported history of patellofemoral symptoms because the exercise program delivered to the intervention group places large loads on this joint. Participants with a previous osteoporotic fragility fracture will be excluded. Those with osteoporosis but no fragility fracture will be eligible. Exclusion criteria include active non-arthritis joint disease (e.g., gout); conditions that might be exacerbated (e.g., unstable angina); neurological conditions such as a stroke; leg trauma within 3 months; and cancer. Participants will be screened for the American College of

Rheumatology (ACR) criteria for clinical knee or hip OA. However, participants not meeting this criterion will still be eligible to participate.

Recruitment & Sample Size: Participants will be recruited through the research coordinator at McMaster. Administrative personnel at Ford who are not in a supervisory role (i.e., Fitness Centre Manager) will disseminate recruitment posters and an email/verbal script. Both will request that interested employees directly contact the research coordinator. These materials will explicitly state that the decision to participate, or not participate, will not be shared with Ford administration.

Our primary outcome is change in self-reported mobility on the Lower Extremity Functional Scale (LEFS). Self-reported mobility is critically important from the patient's perspective ¹³ and is likely to see the largest effect of exercise ¹⁴. The minimal clinically important difference (MCID) of the LEFS is 5 points ^{15, 16}. Rehabilitation produces changes of ≥ 10 LEFS points, with an effect size of 0.5¹⁷. Given a Type I error=0.05 on change, n=27 will yield 81% power.

Randomization: An independent research assistant will conduct randomization and concealed allocation. Participants will be randomized to receive either the exercise intervention, or no intervention. After baseline, the independent research assistant will provide each participant with one sequentially numbered, sealed, opaque envelope that identifies the intervention they will receive.

Interventions

Exercise Program: A 12-week exercise intervention will be offered in the workplace. Ford employees will complete their exercise program at Ford in the on-site exercise facility. 20 of the 40 participants will be randomized to the exercise intervention.

A 12-week supervised exercise program designed for OA knees and hips will emphasize strengthening leg muscles with minimal loads. Each exercise program will be 30 minutes and offered at 7:00am (Mon, Tues, Wed, Thurs, Fri). These timeslots will enable participants to exercise at the start of their workday. Participants will be asked to attend 3 or more supervised exercise sessions weekly ¹⁸. Strengthening will focus on "body weight" strategies that we have used previously, such as squats and lunges. A certified yoga instructor will offer exercise modifications and education about anatomy, OA, and proper lower limb alignment. Over 12 weeks, the exercises will be progressed. These exercises yield nominal loads while increasing leg strength ¹⁹. Our previous randomized controlled trial of this intervention (n=31), delivered within the community, yielded improvements in pain, mobility and self-reported physical function without adverse events.

Control Program: 20 of the 40 participants will be randomized to the control group. These participants will be asked to refrain from changing any interventions or activity existing at baseline over the 12-week intervention period. Afterwards, these participants will be offered the same exercise program free of charge.

Outcome Measures

Outcome measures will be collected at baseline and immediately after the 12-week exercise program.

Primary Outcome: The primary outcome is the change between baseline and follow-up on the LEFS ^{16, 20, 21}. The LEFS consists of 20 items on an adjectival scale that assess difficulty during mobility tasks ranging from transfers to running. This range avoids ceiling and floor effects. It is reliable and valid in OA and has superior sensitivity to change compared to similar measures ^{17, 21, 22}.

Secondary Outcomes

- *Pain:*
 - The Intermittent and Constant Osteoarthritis Pain (ICOAP) self-report questionnaire consists of two subscales: constant and intermittent pain ²³. Data from the ICOAP demonstrate excellent test-retest reliability, internal consistency, and criterion validity in knee and hip OA ²⁴. The ICOAP shows responsiveness following physiotherapy ²⁵.
 - As well, we will collect the Knee/Hip injury and Osteoarthritis Outcome Score (K/HOOS) ²⁶. The K/HOOS is a patient-administered, 42 item questionnaire. Study participants are asked to answer questions on a 5-point Likert scale, which takes approximately 10 minutes to complete. The K/HOOS consists of 5 subscales: pain, other symptoms, activities of daily living (ADL), function in sport and recreation and knee-related quality of life (QOL). The questionnaire results in a normalized score out of 100 for each subscale, where 100 indicates no symptoms and 0 indicates extreme symptoms. The questionnaire relies on subject's recall from the previous week ²⁶.
 - Participants will also complete the Disabilities of the Arm, Shoulder, and Hand (DASH) questionnaire. This 30-item questionnaire addresses upper extremity physical function and symptoms ²⁷.
- *Physical Capacity:*
 - The strength (peak torque) developed during extension and flexion of the hip and knee during maximum voluntary isometric contractions (MVICs) will be measured using a hand-held dynamometer. The peak value for each of knee and hip extension and flexion will be extracted. The reliability scores for these data are excellent ²⁸.
 - Peak grip strength will also be captured using a hand-held dynamometer because grip strength is related to disability, morbidity and mortality ²⁹.
 - In addition, participants will be asked to complete a treadmill walking submaximal fitness test. Maximal oxygen uptake (VO₂max) is the best measure of cardiovascular fitness and is a good indicator of health status ³⁰. This test requires exposure to no more than 85% of maximum heart rate. It is ideal for assessing fitness of people not accustomed to maximal intensity exercise and has produced valid, reliable data in older women ³¹.
- *Mobility:* The mobility performance measures selected reflect the core set of mobility measures recommended by the Osteoarthritis Research Symposium International (OARSI) ³².
 - Six-Minute Walk Test (6MWT) - The 6MWT is used to quantify walking ability. The 6MWT is an inexpensive clinical tool that involves recording the distance that participants cover while walking indoors at their own pace for 6 minutes. Participants are free to stop or use a mobility aid to complete the walking task, making this measure clinically useful. The 6MWT measurement will be recorded indoors in a well-lit, tiled rectangular hallway. The score recorded is the total distance traveled in 6 minutes. Instructions for the 6MWT will correspond with the published protocol ³³. The 6MWT yields highly reliable (intraclass correlation coefficient=.96) and valid data ³⁴.
 - Stair Climbing - Participants will be asked to ascend and descend a 9-step staircase as quickly as possible, without compromising their safety. The hand rail can be used as needed. The participants will be asked to start at the base of the stairs at a distance from the first step of their choosing. The participants will be instructed not to run or jog, and not to skip any steps. Time to ascend and descend will be recorded separately, to the nearest 10th of a second, using a stopwatch. Participants will be asked to repeat this procedure two times, where scores from only the ascent and descent on the second attempt are recorded.

Data from our laboratory demonstrate excellent test-retest reliability of the stair ascent and descent tasks among 29 adults (ICC=0.881, 0.843 respectively).

- 30-Second Chair Stand Test - The 30 second chair stand task quantifies the number of sit-to-stand movements that can be completed within 30 seconds, starting from a seated position in an armless chair of a standard height (45 cm). After an opportunity to practice the task, participants will be asked to perform this task at a comfortable pace. Knee extensor strength is a strong predictor of performance on repeated chair stand tests ³⁵. In addition, lower extremity muscle power was predicted from performance of the 30 second chair stand in 14 older adults ³⁶.
- *Resilience*: To reflect the ability to adapt to stress and adversity, we selected measures of resilience, work ability, and depression.
 - The Resilience Scale (RS) is a 25-item questionnaire that captures information about personal competence and acceptance of life and self ³⁸. This questionnaire produces data that are reliable and show good concurrent validity ³⁸.
 - The Work Ability Index (WAI) is a widely-used self-report questionnaire that consists of seven dimensions including current work ability relative to life-time best, work ability related to job demands, number of current physician-diagnosed health conditions, estimated work impairment due to the conditions, sick leave over the past year, own prognosis, and mental resources ³⁹. The WAI produces reliable data ³⁹.
 - Depressive symptoms will be assessed with the Center for Epidemiologic Studies—Depression (CES-D) Scale, a 20-item scale with emphasis on affect (mood, guilt, worthlessness, helplessness, appetite) ⁴⁰. Data from the CES-D are valid and reliable in adult and arthritic populations ⁴⁰⁻⁴².
 - Self-efficacy will be measured using the Arthritis Self-Efficacy Scale (ASES). The ASES measures arthritis-specific beliefs regarding perception of performance on certain tasks to cope with the disease ⁴³. The ASES produces both reliable and valid data in knee OA ⁴⁴.

Statistical Analyses: Descriptive statistics will be calculated. A repeated measures analysis of variance will be used to compare the impact of the exercise program on change scores for each outcome measure between the exercise and control groups. Independent analyses will be performed for participants that demonstrated clinical criteria for hip and knee OA.

References

1. Canada S. Population by sex and age group. 2013; <http://www.statcan.gc.ca/tables-tableaux/sum-som/l01/cst01/demo10a-eng.htm>. Available at. Accessed May 15 2014, 2014.
4. Canada AAo. *The impact of arthritis in Canada: Today and over the next 30 years*. 2011.

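### The stated 81% power with n=27 is not tied to the randomised 20 versus 20 comparison; if the effect size of 0.5 is in SDs of change, two-sided power for that comparison is about 34%.

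*Combined protocol and SAP*

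**What the plan says.** Under Recruitment & Sample Size, the protocol makes change in LEFS the primary outcome and states that "The minimal clinically important difference (MCID) of the LEFS is 5 points". It then cites a rehabilitation study for changes of at least 10 LEFS points and an effect size of 0.5, and concludes: "Given a Type I error=0.05 on change, n=27 will yield 81% power".

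The design is set out elsewhere:

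- Inclusion and Exclusion Criteria: "We will recruit 40 participants from Ford".
- Exercise Program: "20 of the 40 participants will be randomized to the exercise intervention".
- Control Program: "20 of the 40 participants will be randomized to the control group".
- Primary Outcome: "The primary outcome is the change between baseline and follow-up on the LEFS", measured at baseline and straight after the 12 weeks.
- Statistical Analyses: a repeated measures ANOVA comparing "change scores for each outcome measure between the exercise and control groups".

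The protocol does not say whether 27 is a total, a per-arm number or a single group. For the power figure it names no test and no sidedness, and it gives no SD and no correlation between visits.

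**The concern.** A reader will take the 81% as the power of exercise versus control on LEFS, because that is the randomised comparison and the primary outcome. The sentence does not describe that comparison. The 27 is neither the 20 per arm nor the total of 40. The 0.5 is described as the change seen after rehabilitation, with no comparator, so it is not shown to be a difference between groups.

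At stake is how the result is read. If real power is much lower than stated, a non-significant LEFS result could be taken as evidence of no benefit when the trial had little chance of showing one. Nor can a reader tell whether a between-group difference of the 5-point MCID is within reach.

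**Working it through.** **Inputs from the documents:** alpha 0.05; effect size d = 0.5; n = 27; stated power 81%; 20 per arm; MCID 5 points; rehabilitation change of at least 10 points. **Not given:** sidedness, SD, correlation r between visits, what 27 counts. All power figures below use the exact noncentral t-distribution and assume that everyone contributes both visits.

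**Step 1. Reproduce the stated figure.** For a single-group before-after t-test, the noncentrality is d√n = 0.5 × √27 = 2.60 on 26 df.

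- One-sided, n = 27: **81.2%** (n = 26 gives 79.8%, so 27 is the smallest n reaching 80%).
- Two-sided, n = 27: 70.6%.

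The one-sided version matches. That this was the calculation used is an inference, since the protocol does not name it.

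**Step 2. The planned comparison.** With two visits, the group-by-time F-test (1 df) in the repeated measures ANOVA is the two-sided two-sample t-test on change. Its noncentrality is d√(n₁n₂/(n₁+n₂)). For 20 versus 20 and 0.5 in SDs of change this is 0.5 × √10 = 1.58 on 38 df.

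| Arms | Two-sided | One-sided |
|---|---|---|
| 20 / 20 | **33.8%** | 46.3% |
| 14 / 13 (27 in total) | 23.9% | 35.1% |
| 27 / 27 | 43.8% | 56.7% |

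None of these is near 81%. At 20 versus 20, 80% power needs a difference of 0.91 SD of change two-sided (0.80 one-sided).

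**Step 3. If 0.5 is in raw-score SDs.** With equal SDs at both visits, the SD of change is the raw SD × √(2(1−r)), so d for change is 0.5/√(2(1−r)). At r = 0.8 that is 0.5/√0.4 = 0.79.

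| Assumed r | 0.3 | 0.5 | 0.7 | 0.8 | 0.85 | 0.9 |
|---|---|---|---|---|---|---|
| Two-sided power, 20 / 20 | 26% | 34% | 51% | 68% | 80% | 93% |

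Power reaches 80% at r of about 0.85. The documents give no r.

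**Step 4. In LEFS points, with no SD assumed.** For 80% two-sided power at 20 versus 20, the SD of LEFS change must be no more than:

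- for a 10-point difference: 10/0.909 = 11.0 points;
- for the 5-point MCID: 5/0.909 = 5.5 points.

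**Step 5. In LEFS points, under an assumed SD.** If the change is taken as exactly 10 points and equal to 0.5 SD, the SD is 10/0.5 = 20 points.

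| Reading of SD 20 | SD of change | Detectable at 80% | 95% CI half-width | Power for the MCID |
|---|---|---|---|---|
| SD of change | 20.0 | 18.2 | 12.8 | 12% |
| Raw SD, r = 0.8 | 12.6 | 11.5 | 8.1 | 23% |
| Raw SD, r = 0.9 | 8.9 | 8.1 | 5.7 | 41% |

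Detectable difference = 0.909 × SD of change. Half-width = 2.024 × SD of change × √(1/20 + 1/20). On the raw-SD reading, 80% power for the MCID would need r of about 0.96. These rows are illustrations, because the SD is assumed.

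**The case against.** The strongest reply is that nothing has been miscalculated: 0.5, 0.05 and 27 do give 81% under a recognised test. Other readings also come close:

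- 27 per arm, 0.5 raw SD, r = 0.8, two-sided: 81.3%.
- 27 in total (14/13), 0.5 raw SD, r = 0.9, two-sided: 79.7%; 20 versus 20 then gives 93%.
- Group-by-time effect f = 0.25, correlation 0.6, N = 27: 79.7%; N = 40 then gives 93%.

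If 27 is a required total, recruiting 40 exceeds it, which is ordinary practice. On this view the statement is only incomplete, and 34% is one unfavourable scenario among several.

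Part of this stands. The 81% is not a slip in the sum, the basis of the figure cannot be settled from the text, and 34% holds only for the SD-of-change reading. It is also true that an analysis method is named; what is missing is the test behind the power figure. The two favourable readings at 20 versus 20, however, each need an unstated correlation, and the f = 0.25 reading also gives 0.5 another meaning: it corresponds to a between-group difference in change of 4 × 0.25 = 1.0 raw SD. The reading with 27 per arm does not rescue the claim, because the trial has 20 per arm and power is then 68%. The one match that uses only stated inputs ignores the control group.

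**Conclusion.** The concern holds. The protocol states a power that its planned comparison is not shown to have. If 0.5 is a between-group difference in SDs of change, two-sided power at 20 versus 20 is about 34% (46% one-sided), and 80% power requires 0.91 SD. If 0.5 is in raw-score SDs, two-sided power is 26% to 93% for r from 0.3 to 0.9, a range chosen here because the documents give no correlation. True power is therefore unknown, not established as 34%. Whatever 0.5 means, 80% two-sided power for the 5-point MCID needs an SD of LEFS change of 5.5 points or less. As this is the sole sample-size justification for the primary outcome, it must be corrected.

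**What to change.** Under Recruitment & Sample Size, delete the claim that "n=27 will yield 81% power" and state power for the two-arm comparison of LEFS change. Name the test, the sidedness, the SD of LEFS change with its source, and the assumed between-group difference. A sentence that needs no SD:

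> *With 20 participants per arm and two-sided alpha 0.05, the trial has 80% power for a between-group difference in LEFS change of 0.91 SD of change; power for 0.5 SD of change is about 34%.*

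If the sponsor's 0.5 is in raw-score SDs, say so, state the assumed correlation between visits, and recompute. Add the result in LEFS points once an SD is given. In reporting, read the LEFS result from the between-group estimate and its 95% CI against the 5-point MCID, not from the p-value alone.

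The cost is protocol wording and one sourced SD. Enrolment, allocation and analysis do not change. The restated power may look less favourable than 81%.

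### Cheap improvement: no stratification by OA status is stated, although OA status is screened before allocation and an OA-only analysis is planned, so the arm split in that analysis is left to chance

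*Combined protocol and SAP*

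**What the plan says.** All references are to the combined protocol and SAP.

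- **Inclusion and Exclusion Criteria.** "We will recruit 40 participants from Ford". "Participants will be screened for the American College of" Rheumatology (ACR) clinical knee or hip OA criteria, but "participants not meeting this criterion will still be eligible to participate". The sample is mixed by design, and no expected or minimum number with OA is given.
- **Randomization.** "An independent research assistant will conduct randomization and concealed allocation". After baseline, "the independent research assistant will provide each participant with one sequentially numbered, sealed, opaque envelope that identifies the intervention they will receive". No stratification factor, block size or method of generating the sequence is described.
- **Interventions.** "20 of the 40 participants will be randomized to the exercise intervention", and "20 of the 40 participants will be randomized to the control group".
- **Statistical Analyses.** The arms are compared on each outcome by repeated measures analysis of variance, with no stated adjustment for OA status. Then: "Independent analyses will be performed for participants that demonstrated clinical criteria for hip and knee OA".

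**The concern.** The plan names a subgroup, identifies it at screening and commits to analysing it separately. It is also the group that the introduction is about. Nothing stated in the allocation keeps the arms of that subgroup balanced: a fixed 20:20 total balances the whole sample only. If few participants have OA, the OA-only comparison could be made between quite unequal arms.

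A second, milder consequence falls on the overall comparison. If workers with and without OA differ in how much they can improve on the Lower Extremity Functional Scale or the pain scales, a chance difference in OA share between arms adds noise, and no adjustment for it is stated.

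An unlucky split cannot be undone after allocation, so the question has to be settled before the first envelope is opened.

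**Working it through.** **Inputs.** From the documents: 40 participants, 20 per arm, effect size 0.5 (Recruitment & Sample Size). Assumed: the number with OA, K, which the documents do not give (8 to 30 shown); that the 20:20 total is met exactly without strata; a second effect size of 1.0, for illustration.

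**The plan's own figure.** The plan gives no figure for the OA subgroup. Its 81% power at n=27 reproduces as a one-sided test of change within one group (81.2%), so it says nothing about OA participants compared between arms.

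**Step 1, chance of an uneven split.** Let a be the number of OA participants in the exercise arm. With 20 of 40 drawn and K having OA, a is hypergeometric: P(a) = C(K,a)·C(40−K,20−a)/C(40,20). For K=10, a split of 3:7 or worse has probability 2 × (0.10425 + 0.02824 + 0.00396 + 0.00022) = 27.3%.

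**Step 2, information kept.** Relative to an equal split this is 4a(K−a)/K². Since a has mean K/2 and variance (K/4)(40−K)/39, the average loss is (40−K)/(39K). For K=10: 30/390 = 7.7%.

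**Step 3, power.** Two-sample t-test, two-sided 5%, exactly balanced against the average over unstratified allocations.

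| K | 2:1 or worse | Average information loss | Power at d=0.5, balanced / unstratified | Power at d=1.0, balanced / unstratified |
|---|---|---|---|---|
| 8 | 23.5% | 10% | 9.2% / 8.8% | 22.3% / 20.5% |
| 10 | 27.3% | 8% | 10.8% / 10.3% | 28.6% / 26.8% |
| 12 | 30.1% | 6% | 12.3% / 11.9% | 34.7% / 33.0% |
| 16 | 10.5% | 4% | 15.4% / 15.0% | 46.1% / 44.7% |
| 20 | 2.6% | 3% | 18.5% / 18.2% | 56.2% / 55.1% |
| 30 | under 0.1% | 1% | 26.2% / 26.1% | 75.3% / 74.9% |

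The 2:1 column does not fall smoothly, because the cut-off lands on different whole numbers. The information loss falls steadily and is the better guide.

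**Step 4, what one bad draw costs.** For K=10, the standard error relative to 5:5 is √[(1/3+1/7)/(2/5)] = 1.09 for a 3:7 split and √[(1/2+1/8)/(2/5)] = 1.25 for 2:8.

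**Step 5, overall comparison.** With K=20, the arms differ by four or more OA participants (8:12 or worse) with probability 2 × P(a ≤ 8) = 2 × 0.1715 = 34%.

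**Step 6, after stratifying.** With two series in random blocks of 4 and 6 (assumed sizes), simulation gives an OA arm difference of at most 2 for every even K shown, so 3:7 among 10 cannot occur. For odd K a difference of 3 is possible but rare. It needs a block of 6 cut after three places, all to the same arm: for K=9, 0.5 × 0.5 × 0.1 = 2.5%. Whole-trial totals are usually no further apart than 19:21 and reach 18:22 in about 2–3% of allocations.

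**The case against.** The strongest reply is that the gain is slight. At the plan's own effect size, balance adds about half a percentage point of power or less, and the OA-only comparison is weak even when perfectly balanced (10.8% power with 10 OA participants, 26.2% with 30). A 2:1 split is a mild departure: it raises the standard error by about 6%. If half or more of the sample has OA, such a split is rare, and recruiting for a programme designed for OA might attract many such people; the documents do not say. The OA analysis is one unpowered sentence, the stated purpose also covers workers without joint pain, and unstratified randomisation is legitimate in a 40-person trial at one site. All of this stands, and it limits the point to an inexpensive improvement.

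A reader might infer more than the documents support:

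- **That an uneven split biases the OA-only result.** It does not. Allocation within the OA group is still random, so the loss is one of precision.
- **That the subgroup is likely to be badly lopsided.** This depends on an OA count that is not given. The chance of 2:1 or worse runs from about 30% to under 0.1% over the assumed range.
- **That a single unstratified list is definitely used.** The Randomization section is silent on strata, blocks and sequence generation. It neither describes nor rules out stratification.
- **That stratifying would make the OA analysis informative.** It fixes the split, not the size of the subgroup.

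The reply does not remove two things: protection against a single bad draw, which average figures hide, and better OA balance in the overall comparison.

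**Conclusion.** The point holds as a cheap improvement. No stratification by OA status is stated, although that status is already screened and a separate OA analysis is planned. Over 8 to 30 OA participants of 40, the average information loss is 10% falling to 1%. The figures rest on the assumed OA count and a fixed 20:20 total. If the plan means to analyse hip and knee OA separately, each group is smaller and the chance of an uneven split is greater. The validity of the trial is not in question. The case for acting is that the remedy is standard, uses information already collected, and is available only before allocation starts.

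**What to change.** In the Randomization section, state that ACR knee or hip OA status is recorded before the envelope is handed over, and that two sequentially numbered envelope series are used: one for participants meeting either criterion, one for all others. Each series should be in randomly permuted blocks of varying size, prepared and held by the independent research assistant, with block sizes not disclosed to those enrolling. If stratification is already intended, one sentence saying so is enough.

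The cost is a second set of envelopes and no new assessment. Arm totals may depart from exactly 20:20, so the two sentences that fix 20 per arm should be reworded as a 1:1 target. The two series protect the combined OA group; they do not guarantee balance within hip OA and knee OA separately. The OA-only results should still be presented as imprecise, with the number of OA participants per arm reported.

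### The 30-second chair stand is described and justified as a test of capacity but performed at a comfortable pace, so a change in the count cannot be read as a change in capacity

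*Combined protocol and SAP*

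**What the plan says.** Under Secondary Outcomes, Mobility, the protocol says that the 30-second chair stand "quantifies the number of sit-to-stand movements that can be completed within 30 seconds". After a chance to practise, "participants will be asked to perform this task at a comfortable pace". Two supporting statements follow directly: "Knee extensor strength is a strong predictor of performance on repeated chair stand tests", and "lower extremity muscle power was predicted from performance of the 30 second chair stand in 14 older adults". No other section returns to the pace of this test or says whether preferred pace or best performance is meant.

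Three other parts of the plan bear on the point:

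- **Neighbouring mobility tests.** The stair test asks for the fastest ascent and descent that is safe. The six-minute walk test (6MWT) is self-paced.
- **Physical Capacity.** Hip and knee strength "during maximum voluntary isometric contractions (MVICs) will be measured using a hand-held dynamometer", so strength has its own direct measure.
- **Statistical Analyses.** Change scores are compared between the exercise and control arms for every outcome, which includes the chair stand.

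**The concern.** The description and the rationale both point to what a participant is able to do. The instruction asks for what a participant prefers to do. A person who could do more stands but is comfortable doing fewer is scored on the fewer.

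What is at stake is the interpretation of one secondary result. If the exercise arm gains more stands than the control arm, the description and rationale invite the reader to conclude that leg capacity improved. The count as instructed does not support that step. Nor does the absence of a difference show that capacity was unchanged, because participants may become more capable and still keep the same comfortable tempo.

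**Working it through.** The documents give no chair-stand mean, standard deviation, expected difference or pace effect. There is no planned figure to reproduce and no numerical effect to compute. The check sets the statements side by side and then follows the score algebraically.

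**The statements, all from the chair-stand paragraph**

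| Element | Content | Points to |
|---|---|---|
| Description | Stands that can be completed in 30 seconds | Capacity |
| Instruction | Comfortable pace, after practice | Preference |
| Support 1 | Knee extensor strength | Capacity |
| Support 2 | Leg muscle power, 14 older adults | Capacity |

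**The score**

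1. Let T be the time a participant takes per stand. The count is N = 30/T, so the tempo fixes the score.
2. Let M be the most stands the participant could do in 30 seconds, and p the fraction of that maximum used at the chosen pace, with p at most 1. Then N = p × M.
3. From baseline (0) to follow-up (1), the ratio of counts is N1/N0 = (p1/p0) × (M1/M0). The first factor is preference and the second is capacity. The count alone cannot separate them.
4. Three cases follow:
   - If M1 = M0 and p1 > p0, the count rises with no gain in capacity.
   - If M1 > M0 and p1 = p0 × M0/M1, then N1 = N0 and a real gain is hidden.
   - If p1 = p0, the change is p × (M1 − M0). It has the right sign but is scaled by p.
5. A difference between arms in mean change would follow capacity only if p were stable over the 12 weeks in both arms. The documents neither state nor support this.

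**Could p move differently by arm?** It is possible. The exercise arm is asked to attend three or more supervised sessions a week for 12 weeks, with squats among the exercises, while the control arm is asked to keep its existing activity. What feels comfortable in a sit-to-stand movement may shift in the exercise arm in either direction. The documents do not say that it does, or by how much.

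**The case against.** The strongest reply is that nothing here is contradictory. The first sentence defines the score and the second gives the test condition, so the outcome is simply the number of stands at a comfortable pace. The test sits under Mobility and not under Physical Capacity, and a preferred-pace count is a legitimate mobility measure. A faster comfortable pace may itself be partly a real benefit. The protocol treats the walk test in the same way: "The 6MWT is used to quantify walking ability", by "recording the distance that participants cover while walking indoors at their own pace for 6 minutes". Leg power is not a named outcome, so the trial does not depend on the chair stand to deliver it.

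Much of this stands. Self-pacing is not wrong in itself, and the sentences can be read together. But that reading leaves the strength and power rationale without support, because the documents do not say that those links hold at a comfortable pace. The test's own paragraph offers no other rationale. The introduction to the Mobility section does cite a recommended core set, but what that source prescribes for pace cannot be checked from the documents.

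Three stronger readings are tempting and are not supported:

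- **That a maximal instruction would reduce bias from knowledge of arm.** The envelope is handed over after baseline and the comparator is no intervention, so participants know their arm at the second test. This applies to all the performance tests, and a maximal test also depends on effort. The documents do not show that the bias would be smaller.
- **That the comfortable-pace count is unreliable.** The plan states that "The 6MWT yields highly reliable (intraclass correlation coefficient=.96) and valid data" and gives ICCs of 0.881 and 0.843 for stair ascent and descent, but none for the chair stand. A missing figure is not evidence of poor repeatability, and it says nothing about comfortable versus maximal pace.
- **That the instruction departs from the cited recommendations or validation studies.** Those sources are not in the documents, and the point does not rest on them.

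**Conclusion.** The point holds as a minor one. The chair-stand instruction does not match the test's own description and rationale, and no other section reconciles them. As written, a difference between arms in change cannot be attributed to capacity, and a null result cannot rule out a gain in capacity.

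The size and direction of any distortion cannot be derived from the documents. The conclusion rests only on the fact that tempo determines a fixed-time count, and on the absence of any statement that preferred pace is the intended construct.

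A reader might infer that the outcome is invalid or that the trial's mobility findings are compromised. The documents do not support that. The chair stand is one of 13 secondary instruments by a count of the list (ICOAP, K/HOOS, DASH, leg strength, grip, treadmill test, 6MWT, stairs, chair stand, RS, WAI, CES-D, ASES). Mobility is also covered by the walk and stair tests and by the LEFS, and the primary analysis and the sample size are unaffected.

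**What to change.** Before baseline testing starts, replace the comfortable-pace sentence with an instruction to complete as many full stands as the participant safely can in 30 seconds. This is in line with the stair test in the same section. Keep the wording unchanged at follow-up, because a change between visits would itself confound the change score. The cost is one sentence, with no extra staff, time or equipment. The downside is a somewhat more effortful test.

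If comfortable pace is deliberate, leave the instruction as it is, remove the strength and power rationale, reword the description so that it does not imply capacity, and report the count as preferred-pace mobility only. This costs an edit to one paragraph and gives up any inference about leg strength or power from this test. It is also the route to take if baseline testing has already begun.
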